Dosage/Dose Regimen/ Instillation/Application/Use:	
Subjects eligible to be randomized will receive one of the following treatments to be administered bilaterally twice daily (BID) for 28 days (from Visit 2 to Visit 7).
 
[REDACTED]
 
During a 7-day study run-in period (for the purpose of subject selection) prior to randomization, all subjects will receive Placebo Ophthalmic Solution (Vehicle) bilaterally BID.

Summary of Visit Schedule:	
6 visits over the course of approximately 5 weeks
 
 • Visit 1 = Day -7 ± 1, Controlled Adverse Environment (CAE[®]) Screening • Visit 2 = Day 1, CAE[®] Confirmation / Baseline • Visit 3 = Day 2 ± 2 hours, 24 h recovery post-CAE[®] • Visit 4 = Day 4 ± 2 hours, 72 h recovery post-CAE[®] • Visit 5 = Day 8 ± 1 day, 1-Week CAE[®] Follow-Up • Visit 6 = Day 15 ± 1 day, 2-Week CAE[®] Follow-Up • Visit 7 = Day 29 ± 1 day, 4-Week CAE[®] Follow-Up and Study Exit
Measures Taken to Reduce Bias:	This is a randomized treatment assignment, double masked study
Study Population Characteristics:	
Number of Subjects:	Approximately 300 subjects will be screened to enroll 150 (50 per treatment arm) subjects

Condition/Disease:	Dry Eye Disease
Inclusion Criteria:	
Subjects must:	

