Multiplicity Considerations	

Hierarchical fixed sequence testing will be used to maintain the type I error rate of [REDACTED]. The primary analysis will first evaluate the difference in the change in the total corneal fluorescein staining score from baseline (Visit 2, pre-CAE®) to Visit 7 (Day 29, pre-CAE®) between high-dose ST-100 and placebo. If the results are statistically significant in favor of high-dose ST-100 over placebo [REDACTED], then the study will be considered a success and high-dose ST-100 will be declared to be superior to placebo. Following the hierarchical fixed sequence testing, the following endpoints will be formally tested:
 
1. If the results of total corneal fluorescein staining score from baseline to Visit 7 (Day 29, pre-CAE®) between high-dose ST-100 and placebo are statistically significant in favor of high-dose ST-100 over placebo [REDACTED], then the difference in the change from baseline (Visit 2, pre-CAE®) of the ocular discomfort score on the Ora Calibra® Ocular Discomfort Scale to Visit 7 (Day 29, pre-CAE®) will then be evaluated in the high-dose ST-100 vs placebo groups.2. If the results of ocular discomfort score are statistically significant in favor of high-dose ST-100 over placebo [REDACTED], then the difference in the change in the total corneal fluorescein staining score from baseline (Visit 2, pre-CAE®) to Visit 7 (Day 29, pre-CAE®) between low-dose ST-100 and placebo will then be evaluated.3. If the results of the total corneal fluorescein staining score change from baseline (Visit 2, pre-CAE®) to Visit 7 (Day 29, pre-CAE®) are statistically significant in favor of low-dose ST-100 over placebo [REDACTED], then the difference in the change from baseline (Visit 2, pre-CAE®) in the ocular discomfort score on the Ora Calibra® Ocular Discomfort Scale to Visit 7 (Day 29, pre-CAE®) between low-dose ST-100 and placebo will then be evaluated.	

Should any primary endpoint in the hierarchical fixed sequence fail to reject the null hypothesis, then all untested endpoints will be evaluated as exploratory endpoints as hypothesis generating comparisons. All primary endpoints will be formally tested using the ITT population with multiple imputation as specified in Estimand 1. All secondary and exploratory endpoints will not be type I error controlled and will be hypothesis generating..

Primary Endpoint Efficacy Analysis

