The dependent variable for the total corneal fluorescein staining and ocular discomfort will be based on intra-subject differences [REDACTED] For the primary analysis of the primary endpoints, subjects without a recorded value at Visit 7 (Day 29) will have missing values multiply imputed as specified in Estimand 1.

The change from baseline at Visit 7 (Day 29) of total corneal staining will be analyzed using an analysis of covariance (ANCOVA) model with terms for change in total corneal staining from baseline and treatment group. The change from baseline at Visit 7 (Day 29) of ocular discomfort will be analyzed using an ANCOVA model with terms for baseline discomfort score and treatment group.

The least squares mean of the intra-subject differences for each treatment group will be presented for the individual analyses with two-sided p-values and 95% confidence intervals.

As a sensitivity analysis, secondary examinations of the primary endpoints will also be presented. The sensitivity analyses of the primary endpoints will use multiple imputation and Last Observation Carried Forward (LOCF) imputation, followed by an ANCOVA. Analyses will also be executed using the PP population with observed/recorded data only.

Secondary Endpoint Efficacy Analyses

The method of analysis for secondary endpoints will be based on the distribution of the individual variable for analysis. Variables recorded on a continuous scale will be analyzed at each visit using two-sample t-tests and Wilcoxon rank sum tests. Each visit and treatment group will be summarized using descriptive statistics for the ITT population with observed data only. Changes from baseline will be summarized by visit and treatment using descriptive statistics and analyzed by visit using ANCOVA models with baseline value and treatment group, two sample t-tests and Wilcoxon rank sum tests on the ITT population with observed data only.

Safety Analyses

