4.0 OVERALL STUDY DESIGN

This is a Phase 2, multi-center, double-masked, randomized, placebo-controlled clinical study. Subjects will be randomized to one of the following treatment arms at Visit 2 (Day 1):

- Low dose ST-100 Ophthalmic Solution: [REDACTED]
- High dose ST-100 Ophthalmic Solution: [REDACTED]
- Placebo Ophthalmic Solution (Vehicle): [REDACTED]

Approximately 150 subjects will be randomly assigned to one of the three groups (1:1:1) to receive either ST-100 Ophthalmic Solution or placebo solution as topical ophthalmic drops administered bilaterally BID for 4 weeks. Subjects, Sponsor, Contract Research Organization (CRO), and site personnel will be masked to treatment assignment.

[figure not shown]
During the 7-day study run-in period prior to randomization, all subjects will receive Placebo Ophthalmic Solution (Vehicle) bilaterally BID.

[figure not shown]
During the screening period, two 90-minute exposures to the CAE® will be conducted to ascertain eligibility to enter the study at Visit 1 (Day -7 ± 1) and Visit 2 (Day 1). Subjects who qualify after the initial screening visit will enter the run-in phase, where they will self-administer vehicle BID for approximately 7 days. Those who qualify at Visit 2 (Day 1) will be randomized to receive study drug in a double-masked fashion for 28 days. Subjects will self-administer drops BID and will complete daily diary assessments as instructed.

The CAE® exposure will occur at Visit 1 (Day -7 ± 1), Visit 2 (Day 1), Visit 5 (Day 8 ± 1), Visit 6 (Day 15 ± 1), and Visit 7 (Day 29 ± 2), with Pre-CAE®, during CAE® and Post-CAE® assessments of ocular signs and symptoms.

At Visit 3 (Day 2 ± 2 h) and Visit 4 (Day 4 ± 2 h), no CAE® exposure will occur but signs and symptoms will be assessed for 24h recovery post-CAE® and 72h recovery post-CAE®. Study drug will be discontinued at Visit 7. Subjects will exit from the study at this visit.

The total number of expected participants, including screen failures, is approximately 300 subjects. A study design flow chart is provided below:

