5.3 INCLUSION CRITERIA

Each subject must:

1. Be at least 18 years of age;
2. Provide written informed consent;
3. Have a reported history of dry eye for at least 6 months prior to Visit 1;
4. Have a history of use or desire to use eye drops for dry eye symptoms within 6 months of Visit 1, except as noted below in [Section 5.4\(6\)](#);
5. Report a score of [REDACTED] on the Ora Calibra® Ocular Discomfort & 4-symptom questionnaire in at least one symptom pre-CAE® at Visits 1 and 2;
6. Have a Schirmer's Test score of [REDACTED] at Visits 1 and 2;
7. Have a conjunctival redness score [REDACTED] according to the Ora Calibra® Conjunctival Redness for Dry Eye Scale in at least one eye pre-CAE® at Visits 1 and 2;
8. Have a corneal fluorescein staining score of [REDACTED] in at least one region (e.g. inferior, superior, or central) pre-CAE® at Visits 1 and 2;
9. Have a sum corneal fluorescein staining score of [REDACTED] based on the sum of the inferior, superior, and central regions, pre-CAE® at Visits 1 and 2;
10. Have a total lissamine green conjunctival score of [REDACTED] based on the sum of the temporal and nasal regions pre-CAE® at Visits 1 and 2;
11. Demonstrate a response to the CAE® at Visits 1 and 2 as defined by:
 - a) Having at least a [REDACTED] point increase in fluorescein staining in the inferior region in at least one eye following CAE® exposure
 - b) Reporting an Ora Calibra® Ocular Discomfort Score [REDACTED] at 2 or more consecutive time points in at least one eye during CAE® exposure
[REDACTED]
[REDACTED]
12. Have at least one single eye satisfy all criteria for 6, 7, 8, 9, 10 and 11 above.

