8.3.2 Visit 1: Day -7 ± 1 – CAE® Screening

All subjects will undergo the following screening assessments:

Pre-CAE®

- Informed Consent/Health Insurance Portability and Accountability Act (HIPAA)
- Demographic Data and Medical/Medication/Ocular History
- Review of Inclusion/Exclusion Criteria
- Urine Pregnancy Test (for females of childbearing potential): Women of childbearing potential must have a negative urine pregnancy test to continue in the study
- Ora Calibra® Ocular Discomfort Scale
- Ora Calibra® Ocular Discomfort & 4-Symptom Questionnaire
- OSDI Questionnaire
- Visual Analog Scale (VAS) Symptom Assessment
- Visual Acuity (ETDRS)
- Conjunctival Redness
- Slit Lamp Biomicroscopy
- TFBUT
- Fluorescein Staining
- Lissamine Green Staining
- At least 15-minute wait between lissamine green staining and Schirmer's test
- Schirmer's test
- At least 15 minute wait between Schirmer's test and CAE® exposure
- Adverse Event (AE) Query

- 90-minute CAE® exposure

Post-CAE®

- Ora Calibra® Ocular Discomfort Scale
- Ora Calibra® Ocular Discomfort & 4-Symptom Questionnaire
- Conjunctival Redness
- Slit Lamp Biomicroscopy
- TFBUT
- Fluorescein Staining
- Lissamine Green Staining
- Intraocular Pressure (IOP)
- Undilated Fundoscopy
- Review of Inclusion/Exclusion Criteria
- Run-in (Vehicle) and Diary Dispensation: Prior to discharge from the study site on Visit 1, subjects will be dispensed sufficient Run-in supply to last until Visit 2 and will be educated in diary recording and self-administration of vehicle run-in. Subjects will be instructed to self-administer one drop BID in each eye until Visit 2. Subjects will be instructed NOT to instill run-in on the morning of their next scheduled study visit (Visit 2).
- AE Query
- Subjects will be scheduled for Visit 2.

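### The readable discomfort ANCOVA adjusts only for the Visit 2 pre-CAE score; a Visit 1 pre-CAE covariate may add precision, once the printed staining covariate is corrected to a baseline score

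*Protocol*

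**What the plan says.** **Discomfort model.** The Protocol Synopsis (Primary Endpoint Efficacy Analysis) states that the Day 29 change in ocular discomfort "will be analyzed using an ANCOVA model with terms for baseline discomfort score and treatment group".

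**Staining model.** The sentence before it gives the staining analysis as an ANCOVA "model with terms for change in total corneal staining from baseline and treatment group".

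**Baseline.** The Synopsis paragraph on multiplicity fixes the reference reading for the first test as the change in "total corneal fluorescein staining score from baseline (Visit 2, pre-CAE®) to Visit 7 (Day 29, pre-CAE®) between high-dose ST-100 and placebo". The discomfort tests use the same two time points.

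**Visit 1 readings.** Protocol 8.3.2 lists the "Ora Calibra® Ocular Discomfort Scale" and fluorescein staining among the Visit 1 pre-CAE procedures, and 8.3.3 repeats both at Visit 2. Inclusion criterion 9 (Protocol 5.3) sets a threshold on the staining sum "based on the sum of the inferior, superior, and central regions, pre-CAE® at Visits 1 and 2". Between the two visits, subjects are in a run-in "where they will self-administer vehicle BID for approximately 7 days".

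**Size.** "Approximately 300 subjects will be screened to enroll 150 (50 per treatment arm) subjects". Protocol 10.3 assumes 10% drop-out.

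**What cannot be read.** SAP section 1 says its methods supersede the protocol's. The SAP baseline definition (9.3), its primary models and imputation methods (14.1.1 and 14.1.2), and the primary analysis text in Protocol 10.4.5 are redacted. SAP section 18 is readable and lists one departure from the protocol, an added analysis of change from Visit 2 post-CAE.

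**The concern.** A single graded reading of a variable sign or symptom is a noisy measure of the subject's underlying level. A second pre-randomisation reading of the same measure can explain more of the Day 29 variation. Here it costs no extra visit or procedure, because it is already on the schedule.

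Precision matters because the arms are small and the four primary tests run in a fixed sequence. A failure at any step makes all later tests exploratory, so the standard error at each step affects every later claim.

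The staining sentence needs attention first. Read literally, the change from baseline is regressed on itself. The fit would be perfect and would leave no treatment effect to estimate. The parallel discomfort sentence suggests a drafting slip, but as printed the first test in the sequence has no baseline covariate to which a second could be added.

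**Working it through.** **Inputs from the documents.** Subjects per arm: 150 / 3 = 50. Completers per arm: 50 × (1 − 0.10) = 45. Confidence intervals are 95% and tests are two-sided. Alpha is redacted, and two-sided 0.05 is assumed.

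**Inputs not in the documents.** No effect size, SD, power or between-visit correlation is readable, so the planned sample size cannot be reproduced. Correlations are assumed over a range. Single-baseline power is set at 80% only to give the gains a scale.

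**Formula.** With the Visit 2 score in the model, analysing the change or the Day 29 score gives the same treatment estimate and residual variance. Let a = corr(Visit 1, Visit 7), b = corr(Visit 2, Visit 7) and c = corr(Visit 1, Visit 2).

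- Residual variance with Visit 2 alone: 1 − b².
- With both: 1 − (a² + b² − 2abc)/(1 − c²).
- Proportional reduction: (a − bc)² / [(1 − b²)(1 − c²)]. This is zero when a = bc, meaning Visit 1 predicts Day 29 only through Visit 2.
- If all three correlations equal r, the reduction is [r/(1 + r)]².

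Worked case, b = 0.5 and c = 0.6. Visit 2 alone leaves 1 − 0.25 = 0.75. With a = 0.45 the reduction is 0.15² / (0.75 × 0.64) = 0.0225/0.48 = 4.7%, leaving 0.715. With a = 0.50 it is 0.04/0.48 = 8.3%, leaving 0.688.

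Power from an 80% start is Φ(2.802/√ratio − 1.960), where ratio = 1 − reduction. Equivalent completers per arm = 45/ratio.

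| a | b | c | Variance reduction | Equivalent per arm | Power |
|---|---|---|---|---|---|
| 0.7 | 0.7 | 0.7 | 17.0% | 54.2 | 86.7% |
| 0.5 | 0.5 | 0.5 | 11.1% | 50.6 | 84.4% |
| 0.3 | 0.3 | 0.3 | 5.3% | 47.5 | 82.1% |
| 0.50 | 0.5 | 0.6 | 8.3% | 49.1 | 83.3% |
| 0.45 | 0.5 | 0.5 | 7.1% | 48.4 | 82.8% |
| 0.45 | 0.5 | 0.6 | 4.7% | 47.2 | 81.9% |
| 0.40 | 0.5 | 0.6 | 2.1% | 46.0 | 80.8% |
| 0.35 | 0.5 | 0.6 | 0.5% | 45.2 | 80.2% |
| 0.30 | 0.5 | 0.6 | 0.0% | 45.0 | 80.0% |

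**Effect of eligibility selection.** Thresholds at both visits narrow the range of the covariates and weaken their correlations. A simulation of 2 million normal triples with equal correlations kept only those above −0.5 SD at both visits, which is 52% to 58% of them. The reduction fell from 5.3% to 2.9% (r = 0.3), from 11.1% to 7.1% (r = 0.5) and from 17.0% to 12.4% (r = 0.7). A stricter cut at the mean, keeping 30% to 37%, gave 2.4%, 5.9% and 10.9%. The trial's actual cut-offs are redacted.

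**Cost if Visit 1 is uninformative.** In a two-arm comparison of 90 completers, residual degrees of freedom go from 87 to 86. Chance imbalance on a useless covariate raises the expected variance by about 86/85 − 1 = 1.2%, which moves power from 80.0% to 79.5%. Reductions below about 1% are therefore no net gain.

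**The case against.** **The governing text is hidden.** The SAP overrides the Synopsis, and its model sections are redacted, so a Visit 1 term, or a corrected staining covariate, may already be there. This stands as a limit. That SAP section 18 does not mention such a term is only weak evidence of absence. The SAP also adds Visit 6 to the drop comfort endpoint and drops Visit 4 from discomfort during CAE, and section 18 lists neither.

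**One baseline is a legitimate choice.** The post-run-in, pre-randomisation reading is the natural baseline. Visit 1 comes before a week of vehicle, so it may track Day 29 less well. Both points stand. No bias, type I error or estimand problem follows from using Visit 2 alone.

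**The size is assumed.** This also stands. Most of the cases in which Visit 1 predicts Day 29 less well than Visit 2 does give small gains.

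**Stronger readings that the documents do not support.** A reader might infer that precision is definitely lost on all primary comparisons. The correlations are unknown and the gain can be zero. A reader might also infer that the staining model already adjusts for the Visit 2 score, but its printed covariate is the change. Finally, a reader might infer that eligibility guarantees both readings of both endpoints. It does so for staining only. Criterion 5 uses the separate Ocular Discomfort & 4-Symptom Questionnaire, and criterion 11b uses scores taken during CAE exposure. The Visit 1 value on the primary discomfort scale rests on the visit schedule.

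**Conclusion.** The point holds as an optional efficiency gain, with one wording defect to settle first. On the readable text, the discomfort ANCOVA uses only Visit 2 pre-CAE. The staining ANCOVA would do the same once its covariate is corrected from the change to the baseline score. A Visit 1 pre-CAE reading is scheduled for both measures, and no readable passage uses it in a primary analysis.

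The plausible benefit is a fall in residual variance of about 0% to 17%, for assumed correlations of 0.3 to 0.7. With equal correlations and selection at both visits it is about 3% to 12%. It is near zero if Visit 1 adds nothing beyond Visit 2. From an assumed 80% start, the full range is worth 0 to about 7 points of power. These figures rest on assumed correlations, approximate normality, 45 completers per arm and two-sided 0.05. The single-baseline analysis remains valid.

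**What to change.** Before unmasking:

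1. Correct the staining ANCOVA so that its covariate is the Visit 2 pre-CAE total corneal staining score, in the Synopsis and wherever the wording is repeated.
2. In SAP 14.1.1.1 and 14.1.2.1, add the Visit 1 pre-CAE study-eye value of the same measure as a second covariate. Add it to the imputation models in 14.1.1.2 and 14.1.2.2 as well, so that imputation and analysis use the same terms.
3. Keep Visit 2 pre-CAE as the baseline for computing change. The endpoint and estimand are then unaffected.
4. State how a missing Visit 1 discomfort value is handled, since eligibility does not require one. Filling it within the imputation step, without dropping the subject, is enough.
5. Record the added term in SAP section 18.

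The cost is one model term and one degree of freedom, with a worst case of about half a point of power if Visit 1 proves uninformative. If blinded pooled data are available before unmasking, the three correlations can be checked without treatment codes. If the redacted SAP sections already contain the term, no change is needed on that part.

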13.1	Appendix 1: Schedule Of Visits And Measurements.....	45
13.2	Appendix 2: Examination Procedures, Tests, & Evaluations	47
13.3	Appendix 3: Protocol Amendment Summary	62
13.4	Appendix 4: Sponsor And Ora Approvals	67
13.5	Appendix 5: Investigator's Signature.....	68

LIST OF ABBREVIATIONS

AE	Adverse Event
ANCOVA	Analysis of Covariance
BID	Twice Daily
CAE®	Controlled Adverse Environment
CDs	Compact Discs
CFR	Code of Federal Regulations
CRF	Case Report Form
CRO	Contract Research Organization
DED	Dry Eye Disease
ECM	Extracellular Matrix
eCRF	electronic Case Report Form
EP	European Pharmacopoeia
ETDRS	Early Treatment Diabetic Retinopathy Study
FDA	U.S. Food and Drug Administration
GCP	Good Clinical Practice
HIPAA	Health Insurance Portability and Accountability Act
IB	Investigator's brochure
ICF	Informed Consent Form
ICH	International Conference on Harmonisation
IEC	Independent Ethics Committee
IND	Investigational New Drug Application
IOP	Intraocular Pressure
IP	Investigational Product
IRB	Institutional Review Board
ITT	Intent To Treat
IWRS	Interactive Web Response System
LASIK	Laser In Situ Keratomileusis
LOCF	Last Observation Carried Forward
logMAR	Logarithm of the Minimum Angle of Resolution
LPI	Laser Peripheral Iridotomy
MedDRA	Medical Dictionary for Regulatory Activities
MMP	Matrix Metalloproteinase
NCS	Not Clinically Significant
OD	Right Eye
OSDI	Ocular Surface Disease Index
PI	Principal Investigator
PP	Per Protocol
SAE	Serious Adverse Event
SOP	Standard Operating Procedure
TFBUT	Tear Film Break-Up time
TEAEs	Treatment-Emergent Adverse Events
USP	United States Pharmacopeia
VA	Visual Acuity
VAS	Visual Analog Scale
WHO	World Health Organization

1.0 INTRODUCTION

Dry eye disease (DED) is a prevalent chronic eye condition affecting between 5% and 34% of the population worldwide. More than 16 million Americans suffer from DED, including approximately 1 million to 4 million between 65 to 84 years of age (Fiscella 2011, Messmer 2015). Furthermore, the age of onset is decreasing rapidly due to the widespread increase in electronic “screen time” such that teenagers are now more frequently showing signs and symptoms of DED. Symptoms include severe ocular burning, discomfort, pain, and in more severe cases compromised visual function, including symptomatic blurred vision. These symptoms are associated with tear film hyperosmolarity and instability, inflammation, and wounding of the corneal epithelium and the collagen substrate (Bowman’s layer) that is part of the extracellular matrix (ECM) and to which the epithelium adheres and renews. As is now recognized, even the early stages of DED tissue damage penetrates well beyond the surface epithelial layer and involves the ECM, including disruption of the collagen that is contained in Bowman’s layer and the underlying corneal stroma (Shetty, Deshpande et al. 2016).

Epithelial cell apoptosis incites the release of inflammatory cytokines and proteinases, most notably IL-6, IL-8 and matrix metalloproteinases (MMPs). In the eye, MMP-9 partially digests collagen via its collagenase activity leading to structural and functional disruptions in the collagen matrix underlying the corneal epithelium (Baratta et.al., *in press*). Topical anti-inflammatory therapies (e.g., Restasis®, Xiidra®, Cequa™) have been used to interrupt this process, but they act extremely slowly. Full restoration of corneal homeostasis requires a fully regenerated surface epithelium, which first requires the repair of the collagen substrate. Such repaired collagen then shows the tightly structured and organized fibrillar pattern characteristic of native type I collagen, leading to a resumption of the functional activities of collagen in modulating structural integrity of the ocular ECM and in mediating certain signal transduction activities. This restoration of collagen and ECM homeostasis in turn promotes the rapid regeneration of the corneal epithelium (see, e.g., Kivanany et al., 2018; Hapach et al., 2015).

Disruptions in the epithelial basement membrane, which comprises several collagen types, are also a critical part of ocular surface pathology. Disruption in the basement membrane collagen network leads to adverse effects on the integrity of Bowman’s membrane and allows inflammatory cytokines to pass through, increasing inflammatory cell infiltration in the area of the wound (Shetty, Deshpande et al. 2016). In addition to these anatomical and physiological changes, certain changes in cellular signaling activities occur as well. This is both a hallmark and a cause of DED (see, e.g., Baratta et al. (2021, *in press*)).

No topical therapeutic to date fully addresses the collagenase-mediated damage to the collagen-containing ocular surface tissue that is associated with DED. Topical but indirect therapies for treating tissue damage in DED are available (e.g., amniotic membrane implants, soft contact lenses, and topical anti-inflammatories such as those described above) but these indirect topical treatments and anti-inflammatories only allow the body to heal collagen secondarily, slowly and quite unpredictably. Thus, there remains an urgent and unmet medical need for a direct, rapidly acting and therefore more efficacious treatment option with favorable safety and comfort profiles that also will promote actual repair of the ocular tissue damage that is a hallmark of DED.

ST-100, a formulation comprising a synthetic collagen mimetic peptide, is being developed to topically treat the signs and symptoms of DED.

ST-100 is believed to rapidly repair damaged collagen via intercalation into the disrupted collagen and reformation of the native collagen I triple helix.

Currently, the most common prescription therapeutics for DED are topical anti-inflammatories such as Xiidra®, Restasis® and Cequa™. These traditional therapies, however, do not directly treat a major underlying cause and effect of DED – damage to the ocular surface tissue and specifically to the collagen in the ECM within and underlying the corneal epithelium. The Sponsor has therefore sought to identify and evaluate potential therapeutic formulations which directly repair ocular surface tissue damage which would provide a more rapid and enduring relief of symptoms compared to traditional therapeutic approaches. To date such a therapeutic has not been available. ST-100 addresses this gap as it is thought to rapidly repair damaged collagen via intercalation into damaged collagen triple helices, thereby repairing the ocular surface damage that underlies the signs and symptoms associated with DED. It is anticipated that by healing the underlying collagen matrix of corneal tissues, ST-100 will also reduce the necessity for long-term use of traditional anti-inflammatory regimens.

In a non-clinical, proof-of-concept study in mice, application of ST-100 to the wounded eyes of mice was shown to induce significant recovery of the corneal epithelium, stromal matrix and Bowman's layer following lamellar keratectomy compared to phosphate-buffered saline negative controls. Together with corresponding data obtained using *in vitro* models of the corneal epithelium, these results encouraged the Sponsor to examine the potential for use of ST-100 as a topical, rapidly acting therapeutic for DED in humans.

